Sponsor / Sponsor-Investigator	
Sponsor Thim van der Laan AG [name] [name]
 
Investigator University of Applied Sciences Department of Business Economics, Health and Social Care Physiotherapy Graubünden Attn: [name] [name]

Study Title:	The Psychophysiological Effect of Terrestrial Altitude and Normobaric Hypoxia - A Randomized Clinical Trial
Short Title / Study ID:	The Effect of Terrestrial Altitude and Normobaric Hypoxia
Protocol Version and Date:	Version 02 from 01.05.2019
Trial registration:	Cantonal Ethics Committee Zurich
Study category and Rationale	Other clinical trials of category A according to the ClinV (Art. 20)
Clinical Phase:	-
Background and Rationale:	
Research has consistently shown that exposure to extreme environments (i.e., cold, at altitude) can impair cognitive function (Taylor, Watkins, Marshall, Dascombe, & Foster, 2015). For logistical reasons and to control the study set-up in which the test is carried out, studies that want to investigate the effect of "height" are usually carried out in laboratories. By testing under such controlled conditions, researchers can remove any co-founding factors and isolate a specific stressor, allowing them to better understand the mechanisms by which impairment can occur. However, when people are exposed to such environments as "height" in the "real world", they often experience a number of other additional stressors at the same time, which could produce different results compared to laboratory studies. Surprisingly, however, little attention has been paid to the study of these additional stressors in combination (Tipton, 2012).
 
The best example of multiple stressors that occur in combination is when climbing to high altitudes. Although the percentage of oxygen remains constant at different altitudes (20.93%), the air pressure decreases exponentially as the altitude increases. As a result, the oxygen partial pressure in the arterial blood and tissues is reduced (hypoxia), which leads to a deterioration in both physical and cognitive performance.

SUPSI

Objective(s):	The aim of this study is to compare the psychophysiological effects of terrestrial altitude with a normobaric, hypoxic situation.
Outcome(s):	
Primary results:
 
Physiological measurements
 
 - Perfusion of the skin microcirculation (flux) - Blood oxygen saturation (%) - Oxygen saturation of the muscles (%) - Oxygen saturation of the brain (%) - Heart rate (b/min) - Blood pressure (mm/Hg) - Skin temperature (°C) - Lactate (mmol/l) - Creatine kinase (U/L) - Balance test (° & m/sec) - Pain sensation (N) 
Psychological measurements
 
 - Sleep Disorder Questionnaire - Lake Louis Altitude Sickness Questionnaire - Dyspnea questionnaire - State of mind questionnaire - Stanford Sleepiness Questionnaire - Automated, cognitive test battery 
Secondary results:
 
 - Thermal comfort and heat perception
Study design:	Randomized, clinical, crossover study

SUPSI

Inclusion / Exclusion criteria:
	
Inclusion criteria:
 
 - Healthy, adult aged 18 to 50 years - No cardiovascular diseases and/or interventions - no surgical interventions on the cardiovascular system. - No current injuries and/or pain conditions - Regular and sufficient sleep - No terrestrial altitude of 1000 m exceeded in the last month (including flights) - Not exposed to any form of hypoxia in the last month 
Exclusion criteria:
 
 - Age over 50 years - Current injuries of any kind and/or pain conditions - Acute and/or chronic pain conditions - Known general diseases (e.g. diabetes mellitus) - Fear of hypoxia - Fear of heights or sensitivity to terrestrial altitude - Regular intake of medication (including self-purchased medication), with the exception of contraception drugs - Cardiovascular disease or abnormalities - Abnormalities of blood analysis or ECG - Psychological illnesses - Pregnancy / breastfeeding

Preparation
	
Subject recruitment
 
The subject information and declaration of consent are submitted. Questions may be asked. If the subject agrees with the information, he or she will be summoned to the first day of contact.
 
This includes the explanations on site, the signature of the declaration of consent and the completion of the health questionnaire. The pregnancy test must be negative (women only). If all tests are passed, an appointment is made for the intervention.
 
Test Subject Preparation Measurement Day
 
The test subject lies down on a couch in his underwear. This is followed by the 20-minute room acclimatization phase in the same storage. The room temperature is kept as constant and neutral as possible (deviation of $\pm 2^{\circ}\text{C}$).

SUPSI


Measurements and procedures:
	
During the 20-minute acclimatization phase, the application areas are drawn (skin-friendly pen) and the appliances are attached. If necessary, the hypoxia mask is then put on, the treatment is started and the baseline measurements are carried out. After the baseline measurement, the 5-minute step-up task is performed. After this task, the physiological parameters are measured again. These measurements were followed by a 5-minute cold water bath of the hand. Afterwards, the physiological measurements are carried out up to 30 minutes after the cold water bath (5 min interval) and the questionnaires are filled out afterwards. In the terrestrial altitude situation, the test subject spends the night in the Hohsaas mountain restaurant (https://www.hohsaas-bergrestaurant.ch, canton of Valais) and the measurements are repeated the next day.
 
Perfusion of skin microcirculation
 
The perfusion of the skin microcirculation is visualized using the Laser Speckle Contrast Imager (moorFLPI 2, moor instruments, www.moor.co.uk). This measurement is measured during the baseline measurements, after the step-up task and up to 30 min after the cold water bath of the hand (5 min interval).
 
Oxygen saturation of the muscles and brain
 
The oxygen saturation of the muscles and brain is measured non-invasively with a deep tissue oxygenation monitor (moorVMS-NIRS, moor instruments, www.moor.co.uk). For this purpose, adhesive electrodes are attached over the muscle and forehead. This measurement is measured during the baseline measurements, after the step-up task and up to 30 min after the cold water bath of the hand (5 min interval).
 
Oxygen saturation of the blood
 
The oxygen saturation of the blood is measured with a portable pulse oximeter with finger clip probe (Nonin 7500, Nonin medical B.V., Plymouth, USA). This measurement is measured during the baseline measurements, after the step-up task and up to 30 min after the cold water bath of the hand (5 min interval).
 
Blood pressure and heart rate
 
The heart rate is measured with a heart rate belt and an additional 2-point ECG (Actiheart, Camntech Ltd., Cambridge, UK). Blood pressure is determined by means of an electronically automated upper arm blood pressure meter (Boso-Medicus uno). This measurement is measured during the baseline measurements, after the step-up task and up to 30 min after the cold water bath of the hand (5 min interval).
 
Skin temperature
 
Skin temperature is measured via the iButton system (www.ibuttonlink.com). The self-adhesive sensors transmit the information about the skin temperature wirelessly to a computer. Furthermore, the skin temperature is recorded by means of a thermal imaging camera (FLIR). This measurement is measured during the baseline measurements, after the step-up task and up to 30 min after the cold water bath of the hand (5 min interval).

--	--

SUPSI

Measurements and procedures:	
Lactate and creatine kinase
 
The lactate and creatine kinase measurement are carried out by capillary blood measurement (Accutrend, Roche Diagnostic, Rotkreuz, Switzerland & Reflotron, Roche Diagnostic, Rotkreuz, Switzerland). This measurement is measured during the baseline measurements, after the step-up task and up to 30 min after the cold water bath of the hand (5 min interval).
 
Balance measurement
 
The fluctuations of the hull are recorded and evaluated with the Sway Star™ System (www.b2i.info). The Sway Star™ is a measuring instrument that contains gyroscopes. It is attached to a belt that is placed around the patient's waist. The data is evaluated with the associated Sway Star™ software and transferred to the data sheet. This measurement is carried out after the baseline measurement and after the cold water bath immersion of the hand.
 
Pain sensation
 
The pain threshold is measured using a pain pressure algometer (NOD, www.to-nod.com). This measurement is carried out after the baseline measurement and after the cold water bath immersion of the hand.
 
Psychological measurements
 
The psychological measurements (sleep disorder, altitude sickness, dyspnea, state of mind, drowsiness) are evaluated on the basis of written questionnaires.
 
The cognitive test battery consists of 8 tasks (ANAM, US Department of Defence, Vista Life Sciences, USA), which are carried out on a laptop computer.
 
These measurements are carried out after the baseline measurement and after the cold water bath immersion of the hand.
 
Thermal comfort and temperature perception
 
These parameters are measured using a scale. This measurement is carried out after the baseline measurement and after the cold water bath immersion of the hand .
 
Further processing of the data
 
Windows uses Excel for data pooling and the graphical representation of the end data® .

Study Product / Intervention:	Cloud 9
Control Intervention (if applicable):	As a control, the subjects are observed under normobaric and normoxic conditions.
Number of Participants with Rationale:	We limit the number of subjects to n = 24 study participants due to the available financial resources and due to the power analysis carried out.

Study Duration:	June 2019-December 2020
------------------------	-------------------------

SUPSI

Study Schedule:	
June 2019: planned start of measurements
 
December 2020: planned end of measurements

Investigator(s):	
Examiner
 
 - [name]^{1,2,3} - [name]^{1,2,3} - [name]^{1,2} - [name].¹ 
1.) University of Applied Sciences and Arts Southern Switzerland, Department of Business Economics, Health and Social Care, Physiotherapy Graubünden, [name]
 
2.) THIM the International University of Physiotherapy, [name]
 
3.) Vrije Universiteit Brussel, Department of Movement and Sport Sciences, [name]
 
Contact / Director of Studies [name], PhD University of Applied Sciences and Arts Southern Switzerland Department of Business Economics, Health and Social Care Physiotherapy Graubünden [name] [contact] [contact]

Study Centre(s):	
Single Centre Study:
 
University of Applied Sciences and Arts Southern Switzerland Physiotherapy Graubünden [name]

SUPSI

Statistical Considerations:
	
Psychophysiological changes between terrestrial altitude and normobaric hypoxia - a randomized clinical trial.
 
Repeated measures analysis of variance (MANOVA)
 
2 Factors (Physiological Parameters)
 
 - Situation (terrestrial altitude vs. simulated altitude) - Time (baseline, after step-up task, 0, 5, 10, 15, 20, 25, 30 min post-cold water immersion of the hand) 
2 factors (psychological parameters, balance, thermal comfort, temperature perception)
 
 - Situation (terrestrial altitude vs. simulated altitude) - Time (baseline, post-cold water immersion of the hand) - 
The significance level is set at $P < 0.05$, and the statistical data analysis is carried out with SPSS V. 26.

GCP Statement:
	
This study will be conducted in compliance with the protocol presented here, the current version of the Declaration of Helsinki, the ICH-GCP, ISO EN 14155 (where applicable), and the Swiss Human Research Ordinance HFV.

SUPSI

Overview of the study

It has already been shown in previous studies that various environmental conditions can change both the physiology and psychology of humans (Taylor et al., 2015). For logistical reasons and due to other scientific considerations such as the comparability of results, investigations such as the investigation of "height" are carried out under laboratory conditions. By testing under such controlled conditions, researchers can remove any co-founding factors and isolate the cause of stress, allowing them to better understand the mechanisms by which impairment can occur. However, when exposed to such "real world" environments, they often experience a number of other additional stressors at the same time, which can also affect their performance. Surprisingly, however, little attention has been paid to the study of these additional stressors in combination (Tipton, 2012).

The best example of multiple stressors that occur in combination is when climbing to high altitudes. Although the percentage of oxygen remains constant at different altitudes (20.93%), the air pressure decreases exponentially as the altitude increases. As a result, the oxygen partial pressure in the arterial blood and tissues is reduced (hypoxia), which leads to a deterioration in both physical and cognitive performance. However, in addition to the stressful effects of hypoxia, there can also be other extreme stressors, such as temperature fluctuations, which are known to significantly affect cognitive function (McMorris, Hale, Barwood, Costello, & Corbett, 2017).

The reduced oxygen level in the blood during exposure at high altitude leads to a disturbance of sleep. This happens through changes in breathing during sleep. Consequently, sleep at altitude is characterized by a reduction in total sleep, sleep efficiency, and sleep quality (de Aquino Lemos et al., 2012).

While both hypoxia and sleep deprivation are reported to have negative effects on cognitive performance at rest, this may not be true when a person is exercising or moving. A light activity (such as a step-up task) may be enough to change the psychophysiological responses. It is known that cognitive performance improves with normoxia with light moderate exercise (Chang, Labban, Gapin, & Etnier, 2012). In addition, there is growing evidence that exercise can even cancel out the negative effects of hypoxia on cognitive performance (Ando et al., 2013; Komiyama et al., 2017). Another point that gives rise to further investigations in the field of hypoxia is the sensation of pain. It has already been shown in previous studies that the sensation of pain differs between normoxic and hypoxic situations (Noel-Jorand, Bragard, & Plaghki, 1996). To the knowledge of the authors, however, there are only limited studies that compare these parameters in a laboratory condition with the reactions in the real world. Many people suffer from lung dysfunction (such as COPD) and are therefore at least partially under hypoxic conditions. With this study, we can contribute to understanding the psychophysiological reactions under hypoxia.

Aim of the study

The aim of this study is to evaluate and compare the psychophysiological changes during terrestrial and simulated altitude. These changes will be investigated after a 5-minute step-up task and after a 5-minute cold water immersion of the hand in a) a normobaric, normoxic situation, b) normobaric, hypoxic situation and c) hypoxic, hypobaric situation.

SUPSI

Abbreviations

CEC	Competent Ethics Committee
GCP	Good Clinical Practice
Ho	Zero hypothesis
H1	Alternative hypothesis
KlinV	Ordinance on Clinical Trials in Human Research
Masl.	meters above sea level
hPa	Hectopascals

SUPSI

Study Schedule

The completion of the measurement series is planned for October 2019, and the completion of the entire project for December 2020.

Table 1: Schedule

	January-February	March	April-June	July-October	November-December
2019			Subject information, screening, planning, data collection	Subject information, screening, planning, data collection	Statistics
2020	Writing the article	Writing the Article	Writing the Article	Publishing the article	Publishing the article

SUPSI

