8.2.1 Experimental intervention

Simulated height: The test subjects are in the laboratory of our institution and are connected to Cloud 9 by means of a mask. The subjects are exposed to a simulated altitude of 3530 m above sea level under normobaric conditions. This intervention is used to determine the psychophysiological effect under normobaric and hypoxic conditions.

Terrestrial altitude: The subjects are at an SAC hut (Bergrestaurant Hohsaas: <https://www.hohsaas-bergrestaurant.ch>) in the canton of Valais at an altitude of 3200 m above sea level. By means of this

SUPSI

exposure, the psychophysiological effect under hypobaric and hypoxic conditions is determined. The test subjects spend a single night in this SAC hut and the measurements are repeated the next day.

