2.1 Preparation of the subject

The subject lies in his underwear on a treatment table for a period of 20 minutes. This is followed by the baseline measurement.

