2.2 Intervention

The subject is then exposed to either the simulated altitude or the normobaric & normoxic situation. Afterwards, a step-up task of 5 minutes and a cold water bath immersion of the hand for 5 minutes is performed. In the terrestrial situation, the subject is measured at the time of arrival at the SAC Hut, as well as the following day after an overnight stay at the SAC Hut. The experimental procedure is therefore illustrated:

[figure not shown]

Illustration of the experimental process

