11.4.2 Primary Analysis

The statistical data analysis will be carried out by [name]. [name] after completion of the data collection of the entire project.

Repeated measures analysis of variance (MANOVA)

2 factors:

Factor 1: Situation (simulated altitude vs. terrestrial altitude)

Factor 2: Time (baseline, after step-up task, 0, 5, 10, 15, 20, 25, 30 min post-cold water immersion of the hand)

Repeated measures analysis of variance (MANOVA)

2 factors:

Factor 1: Situation (simulated altitude vs. terrestrial altitude)

Factor 2: Time (baseline, post-cold water immersion of the hand)

The significance level is set at $P < 0.05$, and the statistical data analysis is carried out with SPSS V. 23.

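### The simulated-session baseline is under hypoxia in the synopsis but before exposure in section 9.2.2; if 9.2.2 is followed, it does not match the terrestrial baseline, which is taken at the hut

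*Combined protocol and SAP*

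**What the plan says.** The order of events in the simulated session is given twice, differently.

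- Synopsis, Measurements and procedures: "If necessary, the hypoxia mask is then put on, the treatment is started and the baseline measurements are carried out". Hypoxia starts, then baseline is measured.
- Section 9.2.2, item 2.1 (Preparation of the subject), after 20 minutes lying down: "This is followed by the baseline measurement". Item 2.2 (Intervention) continues: "The subject is then exposed to either the simulated altitude or the normobaric & normoxic situation". Baseline is measured, then exposure starts.

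The table in section 9.1 lists baseline as the first step in the simulated-altitude column but does not say when the mask goes on.

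For the mountain session, item 2.2 says: "In the terrestrial situation, the subject is measured at the time of arrival at the SAC Hut". The measurements are repeated there the next day. The hut is "in the canton of Valais at an altitude of 3200 m above sea level", and no lowland baseline before the ascent is described.

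The primary analysis (section 11.4.2) is a repeated-measures analysis with "Factor 1: Situation (simulated altitude vs. terrestrial altitude") and "Factor 2: Time (baseline, after step-up task, 0, 5, 10, 15, 20, 25, 30 min post-cold water immersion of the hand"). A second version has two times only, baseline and after the cold-water immersion. Baseline is a level of Time in both. The normoxic control session is not a level of Situation.

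**The concern.** Most of the hypotheses in section 11.1 ask whether an outcome changes at simulated compared with terrestrial altitude. In a two-factor model with baseline as one of the times, a difference in change is the situation-by-time interaction. The power analysis in section 11.2 is also for an interaction.

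That comparison is interpretable only if baseline means the same thing in both sessions. Under the 9.2.2 order, change in the simulated session includes the onset of hypoxia, while change in the terrestrial session does not. The interaction could then be significant because of when baseline was taken, with no difference between the two kinds of altitude. Nothing in the plan would correct this. The control session is outside the model, section 11.4.3 provides no secondary analysis, and the explanations in section 11.1 discuss air pressure, duration of hypoxia, temperature and surroundings but not the exposure state at baseline.

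**Working it through.** **The plan's own figure.** The plan gives no figure for this point. Its one calculation, the required 23 participants in section 11.2, does reproduce. With 3 groups, 14 measurements and f(V) = 0.9, df1 = 2 × 13 = 26, df2 = 2 × (23 − 3 − 13 + 2) = 18, and the noncentrality is 23 × 2 × 0.81 = 37.26. Power is 0.647 at 23 and 0.585 at 22, against a target of 0.6. The point below does not depend on it.

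**Step 1: size of the artefact under the 9.2.2 order.** Let m be the normoxic resting level, D the effect of hypoxia (taken as equal for both altitudes and constant over the session), and t the effect of the step-up and cold-water tasks (equal in both sessions).

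| | Baseline | Each later time | Change |
|---|---|---|---|
| Simulated | m | m + D + t | D + t |
| Terrestrial | m + D | m + D + t | t |
| Difference | −D | 0 | D |

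- Interaction artefact: (D + t) − t = D.
- Main-effect artefact: −D/9 with nine times, −D/2 with two times.

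The documents give no D. For oxygen saturation, assume a fall of 5 to 10 points:

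| Size of D (assumed) | Interaction | Main effect, 9 times | Main effect, 2 times |
|---|---|---|---|
| 5 | 5 | 5/9 = 0.56 | 2.5 |
| 10 | 10 | 10/9 = 1.11 | 5 |

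The last column shows the arithmetic only, since saturation is a nine-time outcome.

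**Step 2: unequal effects.** The simulated session is "The subjects are exposed to a simulated altitude of 3530 m above sea level under normobaric conditions", and the hut is at 3200 m, so equal effects are a null scenario. With effects Ds (simulated) and Dt (terrestrial), the 9.2.2 interaction is (Ds + t) − t = Ds, whatever Dt is. The nine-time main effect is 8Ds/9 − Dt = (Ds − Dt) − Ds/9.

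**Step 3: the synopsis order.** Both baselines are hypoxic and the difference at baseline is 0. The time from mask start to baseline is not stated. If only a fraction g of D has developed by then, and the effect at the hut is complete, the interaction artefact is (1 − g)D.

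**Step 4: false-positive rate.** Simulation with n = 24, alpha 0.05 and 10,000 runs per cell. The altitudes are identical after baseline, and only the simulated baseline is shifted, by d (in SDs of one session's measurement). The interaction was tested with Hotelling's T² on the time contrasts of the within-subject differences. Both d and rho, the correlation of these differences over time, are assumed.

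| Times | rho | d = 0 | d = 0.5 | d = 1 | d = 2 |
|---|---|---|---|---|---|
| 9 | 0 | 4.9% | 12% | 40% | 98% |
| 9 | 0.5 | 5.1% | 22% | 76% | 100% |
| 9 | 0.8 | 4.5% | 51% | 99.5% | 100% |
| 2 | 0 | 4.7% | 21% | 66% | 99.7% |
| 2 | 0.5 | 5.1% | 38% | 91% | 100% |
| 2 | 0.8 | 5.2% | 75% | 100% | 100% |

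At d = 1 the situation main effect (paired t on session means) rejects in 7% to 20% of runs with nine times and 42% to 65% with two. With matched baselines (d = 0) the rates are nominal.

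**The case against.** The strongest reply is that the pre-exposure reading rests on one word. Only the synopsis says when the mask goes on, and it puts that before baseline. The 9.1 table, which lists baseline inside the simulated-altitude protocol and after preparation, fits the synopsis. In item 2.2 the word *then* also covers the control situation, where the participant is already in normoxia, so it may only introduce the intervention block. The illustration of the procedure is missing from the text available and might settle the order. All this is fair. It means that the 9.2.2 order cannot be taken as what will be done. It does not remove the conflict, because an examiner working from 9.2.2 as written would measure baseline first.

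Second, section 11.4.2 names two factors and no deciding effect, and several hypotheses (altitude sickness, dyspnea, drowsiness) concern the presence of symptoms, not change. A reader might infer that the interaction is the prespecified primary test. The documents only imply it. For the main effect with nine times the artefact is small.

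Third, a reader might apply D/2 to every outcome measured twice. The synopsis and sections 5.1, 5.2, 9.1.2 and 9.1.3 place balance, pain, psychological and thermal measures after the baseline measurement, while the 9.1 table lists them within it. If they are taken once exposure has begun, their artefact is smaller or absent, so D/2 is an upper limit.

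**Conclusion.** The point holds as an internal contradiction with a conditional consequence. If section 9.2.2 is followed as written, a hypoxia-sensitive outcome shows a spurious interaction equal to the whole hypoxia effect D. The main effect shifts by D/9 for nine-time outcomes, and by up to D/2 for two-time outcomes if these are also taken before exposure. Under the synopsis order this largely disappears, leaving at most a smaller mismatch if the response has not settled by baseline.

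A reader might conclude that the comparison is biased as planned. The documents do not support that, because they do not say which order governs. Outcomes that barely respond to acute hypoxia have D near zero and are unaffected under either order. The saturation figures rest on an assumed D of 5 to 10 points, and the false-positive rates on assumed d and rho; the documents supply none of these.

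The point should be settled before measurement starts. If the simulated baseline is taken only before exposure, no hypoxic baseline exists to recover later.

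**What to change.** Reconcile the synopsis, the 9.1 table and items 2.1 and 2.2 of section 9.2.2. The exposure state at baseline should be stated for each session and be the same in the simulated and terrestrial sessions that enter the comparison. Record the start of exposure and the clock time of baseline in every session. State also whether the outcomes measured twice belong to the baseline block or follow it.

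If a pre-exposure reading is kept, label it as such and leave it out of the Time factor for simulated versus terrestrial altitude.

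Exact matching of elapsed exposure time is not required. It is not possible for the second hut day, which follows a night at altitude, and section 11.1 already treats duration of hypoxia as a difference between the scenarios.

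The cost is protocol wording and clock times on the data sheet.
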